3 TUMOR RESPONSE EVALUATION AND RESPONSE CRITERIA

3.1 Evaluation of target lesions

Complete Response (CR): Disappearance of all target lesions. Any pathological lymph nodes (whether target or non-target) must have reduction in short axis to < 10 mm.

Partial Response (PR): At least a 30% decrease in the sum of diameters of target lesions, taking as reference the baseline sum diameters.

Progressive Disease (PD): At least a 20% increase in the sum of diameters of target lesions, taking as reference the smallest sum on study (this includes the baseline sum if that is the smallest on study). In addition to the relative increase of 20%, the sum must also demonstrate an absolute increase of at least 5 mm. Note: the appearance of one or more new lesions is also considered progression.

Stable Disease (SD): Neither sufficient shrinkage from the baseline study to qualify for PR nor sufficient increase to qualify for PD, taking as reference the smallest sum diameters while on study.

Special notes on the assessment of target lesions

- **Lymph nodes:** Lymph nodes identified as target lesions should always have the actual short axis measurement recorded and should be measured in the same anatomical plane as the baseline examination, even if the nodes regress to below 10 mm on study. This means that when lymph nodes are included as target lesions, the 'sum' of lesions may not be zero even if complete response criteria are met, since a normal lymph node is defined as having a short axis of < 10 mm.
- **Target lesions that become 'too small to measure' :** All lesions (nodal and non-nodal) recorded at baseline should have their actual measurements recorded at each subsequent evaluation, even when very small (eg, 2 mm). If the radiologist is able to provide an actual measure, that should be recorded, even if it is below 5 mm.

However, when such a lesion becomes difficult to assign an exact measure to then:

- i. if it is the opinion of the radiologist that the lesion has likely disappeared, the measurement should be recorded as 0 mm.
- ii. if the lesion is believed to be present and is faintly seen but too small to measure, a default value of 5 mm should be assigned (note: in case of a lymph node believed to be present and faintly seen but too small to measure, a default value of 5 mm should be assigned in this circumstance as well). This default value is derived from the 5 mm CT slice thickness (but should not be changed with varying CT slice thickness).

Lesions that split or coalesce on treatment: When non-nodal lesions 'fragment', the longest diameters of the fragmented portions should be added together to calculate the target lesion sum. Similarly, as lesions coalesce, a plane between them may be maintained that would aid in obtaining maximal diameter measurements of each individual lesion. If the lesions have coalesced such that they are no longer separable, the vector of the longest diameter in this instance should be the maximal longest diameter for the 'coalesced lesion'.

3.2 Evaluation of non-target lesions

While some non-target lesions may actually be measurable, they need not be measured and instead should be assessed only qualitatively at the time points specified in the protocol.

Complete Response (CR): Disappearance of all non-target lesions and normalization of tumor marker level. All lymph nodes must be non-pathological in size (< 10 mm short axis).

Non-CR/Non-PD: Persistence of one or more non-target lesion(s) and/or maintenance of tumor marker level above the normal limits.

Progressive Disease (PD): Unequivocal progression of existing non-target lesions. (Note: the appearance of one or more new lesions is also considered progression).

- The concept of progression of non-target disease requires additional explanation as follows:
- *When the patient also has measurable disease:* To achieve ‘unequivocal progression’ on the basis of the non-target disease, there must be an overall level of substantial worsening in non-target disease such that, even in presence of SD or PR in target disease, the overall tumor burden has increased sufficiently to merit discontinuation of therapy. A modest ‘increase’ in the size of one or more non-target lesions is usually not sufficient to qualify for unequivocal progression status.
- When the patient has only non-measurable disease: To achieve ‘unequivocal progression’ on the basis of the non-target disease, there must be an overall level of substantial worsening such that the overall tumor burden has increased sufficiently to merit discontinuation of therapy. A modest ‘increase’ in the size of one or more non-target lesions is usually not sufficient to qualify for unequivocal progression status. Because worsening in non-target disease cannot be easily quantified (by definition: if all lesions are non-measurable) a useful test that can be applied when assessing patients for unequivocal progression is to consider if the increase in overall disease burden based on the change in non-measurable disease is comparable in magnitude to the increase that would be required to declare PD for measurable disease: ie, an increase in tumor burden representing an additional 73% increase in ‘volume’ (which is equivalent to a 20% increase diameter in a measurable lesion). Examples include an increase in a pleural effusion from ‘trace’ to ‘large’, an increase in lymphangitic disease from localized to widespread, or may be described in protocols as ‘sufficient to require a change in therapy’. If ‘unequivocal progression’ is seen, the patient should be considered to have had overall PD at that point.

3.3 New lesions

The appearance of new malignant lesions denotes disease progression. The finding of a new lesion should be unequivocal: ie, not attributable to differences in scanning technique, change in imaging modality or findings thought to represent something other than tumor (for example, some ‘new’ bone lesions may be simply healing or flare of pre-existing lesions). This is particularly important when the patient’s baseline lesions show partial or complete response. For example, necrosis of a liver lesion may be reported on a CT scan report as a ‘new’ cystic lesion, which it is not.

A lesion identified on a follow-up study in an anatomical location that was not scanned at baseline is considered a new lesion and will indicate disease progression. An example of this is the patient who has visceral disease at baseline and while on study has a CT or MRI brain ordered which reveals metastases. The patient’s brain metastases are considered to be constitute PD even if he/she did not have brain imaging at baseline.

If a new lesion is equivocal, for example because of its small size, continued therapy and follow-up evaluation will clarify if it represents new disease. If repeat scans confirm that there is a new lesion, then progression should be declared using the date of the initial scan.

3.4 Tumor markers

Tumor markers alone cannot be used to assess objective tumor responses. If markers are initially above the upper normal limit, however, they must normalize in order for a patient to be considered as having attained a complete response.

4 EVALUATION OF BEST OVERALL RESPONSE

4.1 Time point response

A response assessment should occur at each time point specified in the protocol.

For patients who have measurable disease at baseline Appendix Table 1 provides a summary of the overall response status calculation at each time point.

Table 1: Appendix Table 1 - Summary of the Overall Response Status Calculation [Time point response - patients with target (+/-) non-target disease]

Target lesions	Non-target lesions	New lesions	Overall Response
CR	CR	No	CR
CR	Non-CR/non-PD	No	PR
CR	Not evaluated	No	PR
PR	Non-PD or not all evaluated	No	PR
SD	Non-PD or not all evaluated	No	SD
Not all evaluated	Non-PD	No	NE
PD	Any	Yes or No	PD
Any	PD	Yes or No	PD
Any	Any	Yes	PD

4.2 Missing assessments and invaluable designation

When no imaging/measurement is done at all at a particular time point, the patient is not evaluable (NE) at that time point. If only a subset of lesion measurements are made at an assessment, usually the case is also considered NE at that time point, unless a convincing argument can be made that the contribution of the individual missing lesion(s) would not change the assigned time point response. This would be most likely to happen in the case of PD.

4.3 Best overall response: all timepoints

Best response determination in trials where confirmation of complete or partial response IS required: Complete or partial responses may be claimed only if the criteria for each are met at a subsequent time point as specified in the protocol. In this circumstance, the best overall response can be interpreted as in Appendix Table 2.

Table 2: Appendix Table 2 - Best overall response when confirmation of CR and PR required		
Overall Response First Timepoint	Overall Response Subsequent Timepoint	Best overall Response
CR	CR	CR
CR	PR	SD, PD or PR ^a
CR	SD	SD provided minimum criteria for SD duration met, otherwise, PD
CR	PD	SD provided minimum criteria for SD duration met, otherwise, PD
CR	NE	SD provided minimum criteria for SD duration met, otherwise, NE
PR	CR	PR
PR	PR	PR
PR	SD	SD
PR	PD	SD provided minimum criteria for SD duration met, otherwise, PD
PR	NE	SD provided minimum criteria for SD duration met, otherwise, NE
NE	NE	NE

CR = complete response, PR = partial response, SD = stable disease, PD = progressive disease, and NE = invaluable.

^a If a CR is truly met at first time point, then any disease seen at a subsequent time point, even disease meeting PR criteria relative to baseline, makes the disease PD at that point (since disease must have reappeared after CR). Best response would depend on whether minimum duration for SD was met. However, sometimes 'CR' may be claimed when subsequent scans suggest small lesions were likely still present and in fact the patient had PR, not CR at the first time point. Under these circumstances, the original CR should be changed to PR and the best response is PR.

4.4 Special notes on response assessment

When nodal disease is included in the sum of target lesions and the nodes decrease to 'normal' size (< 10 mm), they may still have a measurement reported on scans. This measurement should be recorded even though the nodes are normal in order not to overstate progression should it be based on increase in size of the nodes. As noted earlier, this means that patients with CR may not have a total sum of 'zero' on the case report form (CRF).

Patients with a global deterioration of health status requiring discontinuation of treatment without objective evidence of disease progression at that time should be reported as 'symptomatic

deterioration'. Every effort should be made to document objective progression even after discontinuation of treatment. Symptomatic deterioration is not a descriptor of an objective response: it is a reason for stopping study therapy. The objective response status of such patients is to be determined by evaluation of target and non-target disease as shown in [Appendix Table 1](#) and [Table 2](#).

For equivocal findings of progression (eg, very small and uncertain new lesions; cystic changes or necrosis in existing lesions), treatment may continue until the next scheduled assessment. If at the next scheduled assessment, progression is confirmed, the date of progression should be the earlier date when progression was suspected.

5 ADDITIONAL CONSIDERATIONS

5.1 Duration of response

Duration of overall response: The duration of overall response is measured from the time measurement criteria are first met for CR/PR (whichever is first recorded) until the first date that recurrent or progressive disease is objectively documented (taking as reference for progressive disease the smallest measurements recorded on study).

The duration of overall complete response is measured from the time measurement criteria are first met for CR until the first date that recurrent disease is objectively documented.

Duration of stable disease: Stable disease is measured from the start of the treatment (in randomized trials, from date of randomization) until the criteria for progression are met, taking as reference the smallest sum on study (if the baseline sum is the smallest, this is the reference for calculation of PD).

5.2 Lesions that disappear and reappear

If a lesion disappears and reappears at a subsequent time point it should continue to be measured. However, the patient's response at the point in time when the lesion reappears will depend upon the status of his/her other lesions. For example, if the patient's tumour had reached a CR status and the lesion reappeared, then the patient would be considered PD at the time of reappearance. In contrast, if the tumour status was a PR or SD and one lesion which had disappeared then reappears, its maximal diameter should be added to the sum of the remaining lesions for a calculated response: in other words, the reappearance of an apparently 'disappeared' single lesion amongst many which remain is not in itself enough to qualify for PD: that requires the sum of all lesions to meet the PD criteria. The rationale for such a categorization is based upon the realization that most lesions do not actually 'disappear' but are not visualized because they are beyond the resolving power of the imaging modality employed.

5.3 Use of FDG-PET

While FDG-PET response assessments need additional study, it is sometimes reasonable to incorporate the use of FDG-PET scanning to complement CT scanning in assessment of progression (particularly possible 'new' disease). New lesions on the basis of FDG-PET imaging can be identified according to the following algorithm:

- a. Negative FDG-PET at baseline, with a positive FDG-PET at follow-up is a sign of PD based on a new lesion. Confirmatory CT is recommended.
- b. No FDG-PET at baseline and a positive FDG-PET at follow-up:
 - If the positive FDG-PET at follow-up corresponds to a new site of disease confirmed by CT, this is PD.
 - If the positive FDG-PET at follow-up is not confirmed as a new site of disease on CT, additional follow-up CT scans are needed to determine if there is progression occurring at that site (if so, the date of PD will be the date of the initial abnormal FDG-PET scan). If the positive FDG-PET at follow-up corresponds to a pre-existing site of disease on CT that is not progressing on the basis of the anatomic images, this is not PD.

Reference:

- ¹ Eisenhauer EA, Therasse P, Bogaerts J, et al. New response evaluation criteria in solid tumours: Revised RECIST guideline (version 1.1). Eur J Cancer. (2009); 45:228-247.

APPENDIX 2 MANAGEMENT ALGORITHMS

These general guidelines constitute guidance to the Investigator and may be supplemented by discussions with the Medical Monitor representing the Sponsor. The guidance applies to all immuno-oncology agents and regimens.

A general principle is that differential diagnoses should be diligently evaluated according to standard medical practice. Non-inflammatory etiologies should be considered and appropriately treated.

[figure not shown]
Corticosteroids are a primary therapy for immuno-oncology drug-related adverse events. The oral equivalent of the recommended IV doses may be considered for ambulatory patients with low-grade toxicity. The lower bioavailability of oral corticosteroids should be taken into account when switching to the equivalent dose of oral corticosteroids.

Consultation with a medical or surgical specialist, especially prior to an invasive diagnostic or therapeutic procedure, is recommended.

The frequency and severity of the related adverse events covered by these algorithms will depend on the immuno-oncology agent or regimen being used.

GI Adverse Event Management Algorithm

[figure not shown]
Rule out non-inflammatory causes. If non-inflammatory cause is identified, treat accordingly and continue I-O therapy. Opiates/narcotics may mask symptoms of perforation. Infliximab should not be used in cases of perforation or sepsis.

Updated 05-Jul-2016

Renal Adverse Event Management Algorithm

Rule out non-inflammatory causes. If non-inflammatory cause, treat accordingly and continue I-O therapy

[figure not shown]

Patients on IV steroids may be switched to an equivalent dose of oral corticosteroids (e.g. prednisone) at start of tapering or earlier, once sustained clinical improvement is observed. Lower bioavailability of oral corticosteroids should be taken into account when switching to the equivalent dose of oral corticosteroids.

Updated 05-Jul-2016

Pulmonary Adverse Event Management Algorithm

Rule out non-inflammatory causes. If non-inflammatory cause, treat accordingly and continue I-O therapy. Evaluate with imaging and pulmonary consultation.

[figure not shown]

Patients on IV steroids may be switched to an equivalent dose of oral corticosteroids (e.g. prednisone) at start of tapering or earlier, once sustained clinical improvement is observed. Lower bioavailability of oral corticosteroids should be taken into account when switching to the equivalent dose of oral corticosteroids.

Updated 05-Jul-2016

Hepatic Adverse Event Management Algorithm

Rule out non-inflammatory causes. If non-inflammatory cause, treat accordingly and continue I-O therapy. Consider imaging for obstruction.

Patients on IV steroids may be switched to an equivalent dose of oral corticosteroids (e.g. prednisone) at start of tapering or earlier, once sustained clinical improvement is observed. Lower bioavailability of oral corticosteroids should be taken into account when switching to the equivalent dose of oral corticosteroids.

[figure not shown]
*I-O therapy may be delayed rather than discontinued if AST/ALT \leq 8 x ULN or T.bili \leq 5 x ULN.

**The recommended starting dose for grade 4 hepatitis is 2 mg/kg/day methylprednisolone IV.

Updated 05-Jul-2016

Endocrinopathy Management Algorithm

Rule out non-inflammatory causes. If non-inflammatory cause, treat accordingly and continue I-O therapy. Consider visual field testing, endocrinology consultation, and imaging.

[figure not shown]

Patients on IV steroids may be switched to an equivalent dose of oral corticosteroids (e.g. prednisone) at start of tapering or earlier, once sustained clinical improvement is observed. Lower bioavailability of oral corticosteroids should be taken into account when switching to the equivalent dose of oral corticosteroids.

Updated 05-Jul-2016

Skin Adverse Event Management Algorithm

Rule out non-inflammatory causes. If non-inflammatory cause, treat accordingly and continue I-O therapy.

Patients on IV steroids may be switched to an equivalent dose of oral corticosteroids (e.g. prednisone) at start of tapering or earlier, once sustained clinical improvement is observed. Lower bioavailability of oral corticosteroids should be taken into account when switching to the equivalent dose of oral corticosteroids.

[figure not shown]
*Refer to NCI CTCAE v4 for term specific grading criteria.

[^]If SJS/TEN is suspected, withhold I-O therapy and refer patient for specialized care for assessment and treatment. If SJS or TEN is diagnosed, permanently discontinue I-O therapy.

Updated 05-Jul-2016

Neurological Adverse Event Management Algorithm

Rule out non-inflammatory causes. If non-inflammatory cause, treat accordingly and continue I-O therapy.

Patients on IV steroids may be switched to an equivalent dose of oral corticosteroids (e.g. prednisone) at start of tapering or earlier, once sustained clinical improvement is observed. Lower bioavailability of oral corticosteroids should be taken into account when switching to the equivalent dose of oral corticosteroids.

Updated 05-Jul-2016

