4.3.1.1 Nivolumab Dose Delay Criteria

Nivolumab administration should be delayed for the following:

- Grade 2 non-skin, drug-related AE, with the exception of fatigue
- Grade 2 drug-related creatinine, AST, ALT and/or total bilirubin abnormalities
- Grade 3 skin, drug-related AE
- Grade 3 drug-related laboratory abnormality, with the following exceptions:
 - Grade 3 lymphopenia or asymptomatic amylase or lipase does not require dose delay
 - Grade ≥ 3 AST, ALT, total bilirubin will require dose discontinuation
- Any adverse event, laboratory abnormality, or intercurrent illness which, in the judgment of the investigator, warrants delaying the dose of study medication.

Subjects who require delay of nivolumab should be re-evaluated weekly or more frequently if clinically indicated and resume nivolumab dosing when re-treatment criteria are met.

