4.3.5 Treatment Discontinuation Criteria

Tumor assessments for all subjects should continue as per protocol even if dosing is discontinued.

- Nivolumab treatment should be permanently discontinued for the following:
 - Any Grade 2 drug-related uveitis, eye pain or blurred vision that does not respond to topical therapy and does not improve to Grade 1 severity within the retreatment period OR requires systemic treatment
 - Any Grade 3 non-skin, drug-related adverse event lasting > 7 days, with the following exceptions:
 - ◆ Grade 3 drug-related uveitis, pneumonitis, bronchospasm, hypersensitivity reaction, or infusion reaction of any duration requires discontinuation
 - ◆ Grade 3 drug-related endocrinopathies, adequately controlled with only physiologic hormone replacement do not require discontinuation. Adrenal insufficiency requires discontinuation regardless of control with hormone replacement.
 - ◆ Grade 3 drug-related laboratory abnormalities do not require treatment discontinuation except:
 - Grade 3 drug-related thrombocytopenia > 7 days or associated with bleeding requires discontinuation
 - Grade ≥ 3 drug-related AST, ALT or total bilirubin requires discontinuation*
 - Concurrent AST or ALT > 3x ULN and total bilirubin > 2x ULN

* In most cases of Grade 3 AST or ALT elevation, study treatment will be permanently discontinued. If the investigator determines a possible favorable benefit/risk ratio that warrants

continuation of study treatment, a discussion between the investigator and the BMS Medical Monitor/designee must occur.

- Any Grade 4 drug-related adverse event or laboratory abnormality, except for the following events:
 - ◆ Grade 4 neutropenia \leq 7 days does not require discontinuation
 - ◆ Grade 4 lymphopenia or leukopenia does not require discontinuation
 - ◆ Isolated Grade 4 electrolyte imbalances/abnormalities that are not associated with clinical sequelae and are corrected with supplementation/appropriate management within 72 hours of their onset do not require discontinuation
 - ◆ Isolated Grade 4 amylase or lipase abnormalities those are not associated with symptoms or clinical manifestations of pancreatitis. The Sponsor Medical Monitor designee should be consulted for Grade 4 amylase or lipase abnormalities.
- Any dosing interruption lasting $>$ 6 weeks with the following exceptions:

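### The liver stopping rules in Sections 4.3.1.1, 4.3.3 and 4.3.5 and the Appendix 2 hepatic footnote are not aligned, and no sentence says which governs

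*Combined protocol and SAP*

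**What the plan says.** - **Section 4.3.1.1** (dose delay) takes liver values out of the delay rule for Grade 3 laboratory abnormalities: "Grade ≥ 3 AST, ALT, total bilirubin will require dose discontinuation". It gives no exception and no cross-reference, and does not say whether the discontinuation is permanent.
- **Section 4.3.5** opens with "Nivolumab treatment should be permanently discontinued for the following" and lists, with an asterisk, "Grade ≥ 3 drug-related AST, ALT or total bilirubin requires discontinuation". The asterisk note reads "In most cases of Grade 3 AST or ALT elevation, study treatment will be permanently discontinued". Where the investigator judges that benefit/risk may favour "continuation of study treatment, a discussion between the investigator and the BMS Medical Monitor/designee must occur". The note names neither bilirubin nor Grade 4.
- **Section 4.3.5** also lists, without an asterisk, "Concurrent AST or ALT > 3x ULN and total bilirubin > 2x ULN".
- **Section 4.3.3** repeats permanent discontinuation for combined Grade 2 AST/ALT and bilirubin values that meet the discontinuation parameters.
- **Appendix 2**, hepatic algorithm footnote: "I-O therapy may be delayed rather than discontinued if AST/ALT" is at or below 8x ULN or total bilirubin is at or below 5x ULN. The footnote sets no Medical Monitor condition and mentions neither Section 4.3.5 nor concurrent elevation.
- **Status of the texts.** Section 3.5 says subjects must discontinue for the reasons in Section 4.3.5. Appendix 2 describes itself as general guidance for all immuno-oncology agents. No sentence ranks one over the other for liver values.

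**The concern.** A site with a subject in the affected range can find one passage that stops treatment permanently and another that permits a delay. That is first a patient-safety matter. The numeric limits in the concurrent rule are also the AST/ALT and bilirubin limits in the potential drug-induced liver injury definition of Section 6.6 (which adds further conditions), so the unclear text sits where the protocol itself asks for special attention.

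It also touches what the study reports. Section 8.4.4.1 presents the rate of discontinuation due to events. Section 8.3.2 makes time to resolution and use of immune-modulating medication secondary endpoints. Section 1.1.1 says the 500 added subjects should help clarify how effective the management algorithms are. If sites follow different texts, these descriptions could mix two policies for hepatic events.

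**Working it through.** The plan gives no figure to reproduce here. The check compares the stated limits. Let *a* be AST or ALT and *b* total bilirubin, both in multiples of ULN.

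**1. Concurrent rule against the footnote (document figures only)**

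- Section 4.3.5, concurrent rule: stop if a > 3 and b > 2.
- Appendix 2 footnote: delay permitted if a ≤ 8 or b ≤ 5.

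| Reading of the footnote | Values under both rules | Examples (a, b) |
|---|---|---|
| Narrow: *or* taken as *and* | 3 < a ≤ 8 with 2 < b ≤ 5 | (4, 2.5), (6, 4) |
| Literal: *or* | all a > 3 with b > 2, except a > 8 with b > 5 | also (15, 2.5), (4, 6) |

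On a grid of a = 4, 6, 8, 9, 15 and b = 2.5, 4, 5, 6, all 5 × 4 = 20 points meet the concurrent rule. The footnote also covers 9 of them on the narrow reading and 18 on the literal one. The grid only confirms that the overlap exists; it says nothing about how often such values occur.

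**2. Grade-based rules against the footnote**

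The documents grade by CTCAE v4.0 but do not give its liver cut-offs, so the Grade 3 lower limit is an assumption and is varied. Each limb of the footnote is taken by itself. The width of the overlap is 8 minus the lower limit for AST/ALT and 5 minus the lower limit for bilirubin, or zero if that is negative.

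| Assumed Grade 3 lower limit | Overlap | Width (x ULN) |
|---|---|---|
| AST/ALT 3x | above 3x to 8x | 8 − 3 = 5 |
| AST/ALT 5x | above 5x to 8x | 8 − 5 = 3 |
| AST/ALT 8x or more | none | 0 |
| Bilirubin 2x | above 2x to 5x | 5 − 2 = 3 |
| Bilirubin 3x | above 3x to 5x | 5 − 3 = 2 |
| Bilirubin 5x or more | none | 0 |

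The grade-based overlap therefore depends on the cut-offs. The concurrent overlap in step 1 does not.

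**3. The passages side by side**

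| Situation | 4.3.1.1 | 4.3.5 | Appendix 2 footnote |
|---|---|---|---|
| Isolated Grade 3 AST/ALT | Stop, no exception | Stop in most cases; may continue after discussion | Delay permitted up to its limits |
| Grade 3 bilirubin | Stop, no exception | Stop; not named in the note | Delay permitted up to its limits |
| Concurrent a > 3, b > 2 | Not addressed as such | Stop; no asterisk (4.3.3 repeats it for combined Grade 2) | Delay permitted up to its limits; concurrent elevation not mentioned |

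In the first row, Section 4.3.5 and Appendix 2 both leave room not to stop. They differ in the condition: a case-by-case discussion against a numeric limit. Section 4.3.1.1 differs from Section 4.3.5 in that row because only the latter carries an exception. In the second and third rows the body text gives no exception and the footnote does.

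**The case against.** The strongest reply is that precedence is largely settled. Section 3.5 makes the Section 4.3.5 list mandatory, Section 4.3 bases delay and discontinuation on specific criteria, and Appendix 2 is generic guidance whose footnote only permits. A site that follows Section 4.3.5 breaches nothing in Appendix 2. This carries weight, but it leaves a gap. Section 4.3.5 itself uses *should*, no sentence ranks the texts, and Section 1.1 presents the algorithms as applied uniformly across the programme. Sections 4.3 and 6.7 also send sites to guidelines in the Investigator Brochure. A site that relied on the footnote would depart from Section 4.3.5 without being told so.

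Second, the line in Section 4.3.1.1 can be read as routing liver values out of the delay list and on to Section 4.3.5, not as a separate absolute rule. That is plausible, but the line carries no cross-reference.

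Third, the hepatic algorithm figure is not shown. The grade row to which the footnote belongs is unknown, and the figure may treat concurrent elevation separately. If the footnote belongs to a higher-grade row, combined Grade 2 cases fall outside it. This stands as a limit: the overlap is established on the visible text only. The footnote's own wording does, however, read as an exception to an instruction to discontinue.

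A reader might also infer that the body and the appendix give opposite instructions for every Grade 3 liver value. The note in Section 4.3.5 rules that out for isolated Grade 3 AST or ALT.

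**Conclusion.** The hepatic rules are not aligned and should be reconciled. The clearest case is concurrent elevation, where the overlap follows from the protocol's own numbers: at least AST/ALT above 3x to 8x with bilirubin above 2x to 5x ULN, subject to what the figure shows. Bilirubin is also unaligned if Grade 3 begins below 5x ULN, since the note in Section 4.3.5 does not name it. For isolated Grade 3 AST or ALT, Section 4.3.5 and Appendix 2 differ only in conditions, while Section 4.3.1.1 lacks the exception altogether.

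Two larger claims are not supported. One is that the primary endpoint is compromised because hepatitis is a select adverse event category. Section 8.3.1 defines that endpoint as the incidence of high-grade treatment-related select events, and no discontinuation rule enters it. The effect is on patient safety, on the exploratory discontinuation rate and, possibly, on the description of hepatic event management.

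The other is a count of affected subjects. Applying the Phase 1 rate of Grade 3-4 hepatic events to 1280 subjects gives 4/306 × 1280 ≈ 17. The 1% reported for NSCLC gives about 13, and the 3 mg/kg column gives 2/54 × 1280 ≈ 47. These count all Grade 3-4 hepatic events. They include isolated AST/ALT cases and leave out combined Grade 2 cases, so none of them measures the overlap. The documents give no figure that does.

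No view is taken on which clinical rule is right.

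**What to change.** Reconcile Sections 4.3.1.1, 4.3.3 and 4.3.5 (with its note) and the Appendix 2 hepatic footnote. In doing so:

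- make explicit how each text treats isolated AST/ALT elevation, bilirubin elevation and concurrent elevation, and whether the *or* in the footnote is meant literally;
- cross-reference the passages to one another;
- state which text governs when they differ, including the Investigator Brochure guidelines that Sections 4.3 and 6.7 cite.

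The sponsor's clinical team decides the content. The cost is a wording change and a clarification to sites; the sample size and the planned analyses do not change.
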